12.5.2.2 Sensitivity Analyses

For continuous endpoints to be analyzed using MMRM, no explicit imputation of missing data is needed as the MMRM analysis will be performed on observed cases and implicitly imputes missing data. =

Sensitivity analyses using different ways of handling missing ALP data will be performed for the primary endpoint to assess the impact of missing data and the intercurrent strategy on the primary efficacy results:

- 1. Sensitivity analysis #1 While it is intended that complete data will be recorded at 24 weeks, if there is a significant amount of missing data, the robustness of the primary analysis will be assessed using multiple imputation (Section 12.5.2.2.1)
- 2. Sensitivity analysis #2: If examination of residual plots indicates significant outliers, then ALP data at 24 weeks will additionally be analyzed using a Robust Regression approach after first multiple imputing any missing data (Section 12.5.2.2.2)

12.5.2.2.1 Sensitivity Analysis #1 - Multiple Imputation for Sensitivity Analysis of Primary Endpoint

If missing data are observed following discontinuation, the MMRM will estimate what would have happened had patients not discontinued, and the treatment effect may be biased. To assess the robustness, a multiple imputation approach will be performed where the relationship between ALP data and time from discontinuation will be modelled within each treatment group separately, and using that relationship, data missing post-discontinuation will be imputed based on data observed post-discontinuation in other patients.

The imputation model will include data from baseline and Weeks 2, 4, 8, 12, and 24 and will impute missing ALP values as follows:

 For subjects who discontinue study treatment and who do not have subsequent ALP measurements, the missing data imputation method will use subjects in the same treatment arm who discontinue study treatment and do have subsequent ALP measurements (defined as

Version Date: 27-June-2024

Sponsor: Calliditas Therapeutics Suisse SA

Protocol No: GSN000350

'retrieved dropouts') allowing for how long prior to each visit the subject discontinued. Therefore, if there is some loss of efficacy post discontinuation of therapy, subjects who discontinue study treatment and have missing data will have data imputed based on such a loss of efficacy.

- For subjects who initiate a new PBC medication, all data collected post the commencement of PBC medication will be treated as missing data in the model.
- In the unlikely event that subjects die before a visit, they will have the largest ALP value, observed across treatment arms, imputed at that visit.

The variables to be used in the analysis are described below together with sample SAS® code [Note the actual variable names may vary in the analysis]:

- TRT = treatment group
- VAL1-VAL5 = log-ALP value at each post-baseline visit for Weeks 2,4,8,12 and 24, respectively
- WDAW1-WDAW5 = Time from treatment discontinuation at Weeks 2,4,8,12 and 24, respectively. Covariates will be constructed for each scheduled visit up to Week 24 and depending on the time point being imputed, the corresponding covariate will be used in the imputation model. For example, if Week 24 is being imputed the Week 24 covariate below will be used to determine time from treatment discontinuation in the model. Each WDAW covariate takes a value of 0 if a subject is still receiving therapy at that visit and will be fitted as class variables. The value of the covariates will be derived as follows (the visit windows defined in section 10.3 will be applied):
 - WDAW1 (Week 2 Visit): If the subject discontinued treatment prior to Week 2 Visit set to
 1; otherwise set to 0
 - WDAW2 (Week 4 Visit): If the subject discontinued treatment prior to Week 2 Visit set to
 2; if the subject discontinued IMP on or after Week 2 Visit but prior to Week 4 Visit set to
 1; otherwise set to 0
 - WDAW3 (Week 8 Visit): If the subject discontinued treatment prior to Week 2 Visit set to 3; if the subject discontinued IMP on or after Week 2 Visit but prior to Week 4 Visit set to 2; if the subject discontinued treatment on or after Week 4 Visit but prior to Week 8 Visit set to 1; otherwise set to 0
 - WDAW4 (Week 12 Visit): If the subject discontinued treatment prior to Week 2 Visit set to 4; if the subject discontinued treatment on or after Week 2 Visit but prior to Week 4 Visit set to 3; if the subject discontinued treatment on or after Week 4 Visit but prior to Week 8 Visit set to 2; if the subject discontinued treatment on or after Week 8 Visit but prior to Week 12 Visit set to 1; otherwise set to 0
 - O WDAW5 (Week 24 Visit): If the subject discontinued treatment prior to Week 2 Visit set to 5; if the subject discontinued treatment on or after Week 2 Visit but prior to Week 4 Visit set to 4; if the subject discontinued treatment on or after Week 4 Visit but prior to Week 8 Visit set to 3; if the subject discontinued treatment on or after Week 8 Visit but prior to Week 12 Visit set to 2; if the subject discontinued treatment on or after Week 12 Visit but prior to Week 24 Visit set to 1; otherwise set to 0
- WD = binary covariate indicating whether the subject had discontinued from therapy prior to Week 24 Visit
- USUBJID = Subject ID
- VISIT = Visit name
- CHG = Change of log-ALP baseline ratio at each visit
- BASE = log-baseline ALP

Version Date: 27-June-2024

Sponsor: Calliditas Therapeutics Suisse SA

Protocol No: GSN000350

Using the monotone datasets generated for ALP, the missing ALP data will be imputed separately for each treatment group using a REGRESSION method in conjunction with the MONOTONE statement of the SAS MI procedure. The steps are as follows:

Step 1: is to create data with a monotone data structure. For example, at this stage, data would only be imputed at Week 12 if the subject had data recorded at week 24. This allows subjects with a non-monotone pattern of missing data to be included in the analysis. The imputation model used to create monotone data pattern will include the following factors and covariates: randomized treatment group (TRT), log baseline ALP (BASE), covariate indicating if the subject discontinued treatment prior to Week 24 (WD) and the value of log-ALP at all visits up to Week 24 (VAL 1-VAL5). The WD covariate may be removed from the final model.

```
proc mi data=data nimpute=20 seed=7872228 out=partial;
var BASE WD VAL1-VAL5;
mcmc chain=single nbiter=200 niter=200 impute=monotone;
by TRT;
run:
```

NBITER will be set to 200, so 200 burn-in iterations are created before sampling the first imputed dataset, and NITER also set to 200 so that each subsequent imputation is separated by 200 from the same chain. An autocorrelation plot will be produced to confirm that NITER is long enough to ensure imputations are independent and a trace plot also produced to confirm there are no systematic trends.

Step 2: Missing ALP data will be imputed separately for each treatment arm using a regression model and incorporating time from treatment discontinuation covariates as follows:

The number of imputations will depend on the percentage of missing data to be imputed and will range from a minimum of 5 to a maximum of 50 imputed datasets. The below formula will be used to calculate the number of imputations:

```
Number of Imputations = 5 + 1.5 * (m)
```

where m is the proportion of missing data, expressed as a percentage. The smallest integer greater than or equal to the number will be used for the number of imputations.

Note, individual covariate terms for time from treatment discontinuation may be dropped from the model and/or factor levels removed if a particular pattern of missing data is not present when data are unblinded. In particular, if there are subjects present with missing data for a specific level of one of the covariates for time from treatment discontinuation, but there are no matching subjects with data observed for the same level of the same factor in the same treatment arm, the factor level will be grouped with the next highest level to enable the imputation model to be run (for example Week 2 will be grouped with Week 4). This will require running separate MI procedures if the pattern differs by treatment arm.

In the event that the above model fails, the time from treatment discontinuation covariates may be removed as follows

Sponsor: Calliditas Therapeutics Suisse SA

Protocol No: GSN000350

Proc mi data=partial nimpute=1 seed=439384 out=impute minmaxiter=100000; monotone regression; var BASE VAL1-5; by TRT imputation_; run;

Step 3: the MMRM model is applied to the transposed, imputed data. Any subject who dies prior to a visit will have worst case data imputed only at this stage prior to analyzing the data. Baseline ALP will be included as a covariate and will be calculated as the geometric mean of pre-randomization ALP results, as defined in section 10.1 and log-transformed prior to inclusion in the analysis model. The model will also include terms for treatment group, visit, log(baseline) by visit, and visit by treatment group interaction. Subject will be included as a random effect.

An unstructured covariance matrix will be used to model the within-subject correlation of data. The Kenward-Roger's degrees-of-freedom adjustment will be used. Restricted maximum likelihood will be used to obtain parameter estimates. Model assumptions of the MMRM will be assessed using residual plots (such as q-q plots, histograms, box plots, and scatter plots). If the model above does not converge, heterogeneous Toeplitz covariance structure will be used instead of the unstructured covariance matrix. If convergence still does not meet, the Toeplitz structure will be used.

```
proc mixed data=imputed method=reml;
    class TRT USUBJID VISIT;
    model CHG = TRT VISIT BASE BASE*VISIT VISIT*TRT /ddfm=kr;
    repeated VISIT/ sub = USUBJID type = un;
    lsmeans TRT*VISIT /cl pdiff;
    by _imputation_;
    ods output LSMeans=mixlsmean Diffs=mixdiff;
run:
```

Step 4: In the pooling phase, estimated treatment effects and associated standard errors from each imputation will be combined using Rubin's rules (Rubin, 1987) to provide an overall treatment effect, associated 95% confidence interval (CI), and 1-sided p-value.

```
proc mianalyze data=mixlsmean;
by VISIT;
modeleffects estimate;
stderr stderr;
ods output ParameterEstimates=Ismeans;
run:
```

This analysis will only be performed if there is sufficient data from 'retrieved dropouts' to ensure a reliable model with imputation.

If there are insufficient data after grouping, the imputation model may be updated to reduce the number of covariates or apply a simplified imputation method.

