6.0 Introduction

This SAP should be read in conjunction with the study protocol and case report forms (CRF). This version of the plan has been developed by ICON using the protocol version 5.0 dated 27-Sep-2023 and CRF version 6.0 dated 03-Aug-2023. Any further changes to the protocol or CRF that have an impact on the design, or the planned statistical analysis will require updates to the SAP.

The TRANSFORM study was initiated as a randomized, placebo controlled, double-blind, adaptive Phase 2b/3 study with a 52-week treatment period and a 52-week open-label extension period. Enrolment into the study has been significantly slower than predicted and the feasibility of conducting the study within an acceptable timeframe has proven challenging. This is considered related to new and more frequently used treatment options, such as obeticholic acid (OCA) and off-label use of fibrates. One consequence of this is that fewer subjects are meeting the inclusion criteria for alkaline phosphatase (ALP) ≥ 1.67*ULN.

Considering the challenges, under protocol version 5.0, the study has been revised to a randomized, placebo-controlled, double-blind, **Phase 2b** study of setanaxib in **60-70** subjects with PBC and elevated liver stiffness, to assess the safety and efficacy of the 1200 mg and 1600 mg doses of setanaxib versus placebo over a **24-week treatment period**. The primary endpoint has been amended to evaluate change in ALP (%) on a continuous scale at 24 weeks, rather than the originally planned (binary) composite endpoint of change in ALP and total bilirubin at 52 weeks which requires a significantly larger sample size. The secondary endpoints of change in fatigue and liver stiffness are retained, as is the composite endpoint of changes in markers of cholestasis. The rationale for a 52-week Extension Phase Treatment Period and for an interim analysis is no longer applicable; therefore, the Extension Period, the 12-week Follow-up Period and interim analysis have been removed. A detailed rationale for changes to the study design is described in Protocol Amendment version 5.0 Section 1.2. The results from this Phase 2b study will inform the future development of setanaxib in PBC.

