8.2 Randomization

The randomization schema remains unaffected by Protocol Amendment version 5.0. Eligible subjects enrolled according to Protocol Amendment version 5.0 will be randomly assigned to oral setanaxib 1200 mg/day, 1600 mg/day, or placebo, according to a 1:1:1 randomization ratio, stratified by Screening serum ALP < or ≥3.0×ULN.

Randomization will be performed via a centralized Interactive Web Response System (IXRS) contracted through Almac. At registration, the IXRS will assign a unique subject identification number that will be used on all of the subject's eCRFs and serious adverse event (SAE) report forms. If a subject is rescreened (see Protocol Amendment version 5.0 Section 4.3), the rescreened subject should be assigned a new unique screening number.

Any subjects who entered the Extension Phase under protocol versions 1.0 to 4.0 will have received the same setanaxib treatment dose they received during the first 52 weeks of study treatment (the Main Part). Subjects initially randomized to placebo will have been switched to setanaxib 1200 mg/day or 1600 mg/day according to a 1:1 randomization ratio in the Extension Phase. Randomization in the Extension Phase was not stratified. All subjects will have had a new randomization number assigned on enrollment into the Extension Phase, even if they were not re-randomized to a new treatment arm; this is to protect the blind for subjects prior to the completion of the double- part of the study.

During the course of the study, the statistician and the programmers supporting the IDMC analysis will be unblinded and will remain separate from the wider project team throughout the life of the study. The randomization will be performed by the external IXRS provider, Almac. The blinded statistician supporting the study will have no access to the unblinded randomization schedule. The Investigator, the site personnel,

Version Date: 27-June-2024 Sponsor: Calliditas Therapeutics Suisse SA

Protocol No: GSN000350

the Sponsor and their representatives involved in monitoring and conducting the study, the Adjudication Committee, and the subjects will be blinded to treatment assignments until the study is unblinded for the primary analysis. For full details refer to the Data Blinding and Documentation plan.

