10.0 Conventions and Derivations

10.1 Baseline and Change from Baseline

10.1.1 Baseline Values for Liver Biochemistry

Baseline values for liver biochemistry (ALP, ALT, AST, total and direct bilirubin, and GGT) are determined by the geometric mean of the last (up to) 3 measurements preceding the first administration of study drug. This includes unscheduled and screening visits. The formula for the geometric mean (GM) given three measurements a, b, and c is expressed as follows:

$$GM = \exp(\log(a) + \log(b) + \log(c)/3)$$

For subjects who have records for both Screening/Visit 1 and Baseline Visit 3, the baseline will be calculated as the geometric mean of these two values. If there is an additional unscheduled pre-dose result, the geometric mean will be calculated using up to three values.

For subjects who have records for Screening/Visit 1, Screening/Visit 2, and Baseline Visit 3, the Screening/Visit 1 result should be disregarded due to the subject's re-screening. The baseline should be calculated as the geometric mean of the Screening/Visit 2 and Baseline Visit 3 results. If there is an additional unscheduled pre-dose result, the geometric mean should include up to three values.

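### Sensitivity Analysis #1 scores a death with one fixed ALP level, so on the ratio-to-baseline endpoint the penalty depends on the patient's baseline

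*SAP*

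**What the plan says.** SAP 12.5.2.2.1 builds the multiple-imputation analysis on ALP levels. The variables VAL1 to VAL5 are the "log-ALP value at each post-baseline visit for Weeks 2,4,8,12 and 24, respectively". For a patient who dies before a visit, the rule is "they will have the largest ALP value, observed across treatment arms, imputed at that visit". Step 3 restates it without a scale: "Any subject who dies prior to a visit will have worst case data imputed only at this stage prior to analyzing the data".

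The response analysed in Step 3 is a ratio to baseline, defined as "CHG = Change of log-ALP baseline ratio at each visit", and the model line is "model CHG = TRT VISIT BASE BASE*VISIT VISIT*TRT /ddfm=kr". Baseline is "determined by the geometric mean of the last (up to) 3 measurements preceding the first administration of study drug" (SAP 10.1.1).

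No section turns the largest level into a worst change. None says whether the maximum covers that visit only, all post-baseline visits, or every record including baseline. SAP 12.5.3.2 and Table 5 (SAP 10.18) carry the imputation method over to fatigue and liver stiffness without a death rule for those scales.

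**The concern.** A worst-case rule should give a death a value at least as bad as the worst outcome seen, and roughly equally bad whoever dies. A single ALP level does not do this on a ratio scale. The score for a death is log(maximum ALP) minus log(own baseline), so two patients who die on the same day can get very different scores only because they entered with different ALP.

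Baselines can differ several-fold. The SAP introduction refers to "inclusion criteria for alkaline phosphatase (ALP) ≥ 1.67*ULN", no upper ALP limit is listed among the eligibility criteria, and randomization is "stratified by Screening serum ALP < or ≥3.0×ULN".

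Two things are at stake. An extreme imputed value in one arm enlarges the residual variance that all arms share, which also weakens the comparison of the other dose with placebo. And the adverse weight given to a death becomes arbitrary in the one analysis that gives death an unfavourable value on the continuous ALP endpoint.

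**Working it through.** The SAP states no figure for the effect of this rule, so there is none to reproduce.

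**Inputs from the documents.** Planned reductions are 25% and 2.5%, with SDs of 19% and 24% and 22 enrolled per arm (SAP 8.1). Eligible ALP is at least 1.67×ULN. On the log scale the SDs are √ln(1 + (19/75)²) = 0.249 for setanaxib and √ln(1 + (24/97.5)²) = 0.243 for placebo. The planned ratio of ratios is 0.75/0.975 = 0.769, about −23%.

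**Assumed inputs.** The documents give neither the baseline distribution nor the visit maxima, so I show ranges.

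**Step 1: score of a death.** Score = maximum/baseline − 1, with ALP in ×ULN:

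| Assumed maximum | Baseline 1.67 | 3 | 5 | 8 | 10 |
|---|---|---|---|---|---|
| 5 | +199% | +67% | 0% | −38% | −50% |
| 8 | +379% | +167% | +60% | 0% | −20% |
| 12 | +619% | +300% | +140% | +50% | +20% |

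With a maximum of 8 and a baseline of 1.67, the log ratio is ln(8/1.67) = 1.57. That is (1.57 − ln 0.975)/0.243 = 6.6 SD above the placebo mean. Negative entries need a maximum that excludes the patient's own baseline record.

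**Step 2: effect of one active-arm death on that arm's contrast.** By hand, a maximum of 8 and a baseline of 1.67 shift the arm mean by (1.57 − ln 0.75)/22 = 0.084. The effect becomes 0.769 × e^0.084 = 0.837, or −16.3%. With a worst observed ratio of 1.57, the shift is (ln 1.57 − ln 0.75)/22 = 0.034, giving 0.769 × e^0.034 = 0.796, or −20.4%.

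A simulation used 3,000 trials per row, a Week 24 ANCOVA with log baseline, an assumed baseline median of 2.5×ULN with log SD 0.5 truncated at 1.67, and the visit-specific maximum:

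| Baseline of the patient who dies | Score, SAP rule | Effect (SE) | Score, worst ratio | Effect (SE) |
|---|---|---|---|---|
| 1.67 | +392% | −16.4% (0.102) | +57% | −20.4% (0.079) |
| 4 | +105% | −19.5% (0.084) | +58% | −20.3% (0.079) |
| 8 | +3% | −22.1% (0.076) | +57% | −20.5% (0.079) |
| 12 | −31% | −23.3% (0.075) | +57% | −20.8% (0.079) |

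With the death left out, the effect is about −23% (SE 0.076).

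**Step 3: one random death in the 1600 mg arm.** Assumed baseline medians were 2.2, 2.5 and 3.0×ULN with log SD 0.35, 0.5 and 0.6, and a common log SD of 0.246 for the change.

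- The median imputed change is a 2.2- to 3.5-fold rise. The median worst observed change is about 1.56-fold.
- The imputed change exceeds every observed change in 83% to 90% of trials.
- The SE of the 1200 mg versus placebo contrast rises 14% to 27%. Under the worst-ratio rule it rises about 6%.

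**Step 4: how often a death scores below baseline.** For a random death, with assumed medians of 2.0 to 3.0×ULN and log SD 0.4 to 0.6:

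- Maximum at that visit: 1.6% to 2.2%.
- Maximum over all post-baseline visits: 0.3% to 0.5%.
- Maximum over all records including baseline: 0%. Baseline is a geometric mean of the patient's own pre-dose values and cannot exceed that maximum.

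**The case against.** *Analysing change is not the fault.* This is correct. With BASE and BASE*VISIT in the model, using CHG or log-ALP as the response gives identical treatment contrasts, standard errors and residuals, as a numerical check confirmed. But equivalence of the two responses does not make the largest level a worst case. Either way, the model judges a value against what it predicts from that patient's baseline. One level given to patients with different baselines lies far above the prediction for a low baseline and near or below it for a very high one.

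*A severe penalty is the purpose of the rule.* Also fair, and it works against the arm in which the death occurs. It does not explain why the severity should vary with baseline, or why the dose without a death should lose precision.

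*The analysis is protected and rarely runs.* This stands and limits the size of the point. The SAP calls death before a visit unlikely, and the protocol excludes decompensated disease. The analysis runs only with a significant amount of missing data and enough retrieved dropouts (SAP 12.5.2.2 and 12.5.2.2.1). Residual plots are prespecified, and a forest plot shows the result beside the primary one (Table 7). Formal Hochberg testing rests on the primary analysis (SAP 12.5.1), so a loss of power here changes no decision rule.

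*Death is scored unfavourably elsewhere.* A reader might infer that this is the only place where the SAP does so for ALP. That goes too far. SAP 12.5.4.1 counts patients with an adverse clinical outcome before Week 24 as non-responders for the cholestasis markers, and SAP 10.9 lists death among those outcomes. The statement holds only for the continuous ALP endpoint, where Table 6 labels death as composite but merely excludes later data.

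**Conclusion.** The point holds as a small defect in a stated rule. For a given maximum, the score of a death is fixed by baseline. Low-baseline deaths become outliers that usually exceed any observed change and raise the other dose's SE by about 14% to 27%. Deaths at the highest baselines are penalised little. The records that define the maximum are not stated.

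A reader might infer more: that a death on setanaxib counts as an ALP reduction and flatters the arm. The documents do not support that as a general claim. It is impossible if the maximum covers all records including baseline. It needs a visit-specific or post-baseline maximum, and the wording allows the visit-specific reading without settling it. Even then, scoring below baseline is not enough to improve the contrast: the value must fall below what the model expects for that patient, about 25% under baseline on setanaxib. In simulation under the visit-specific reading, the contrast improves in under 1% of random deaths, and in 4% to 12% when the arm's highest-baseline patient dies.

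The sizes rest on assumed log-normal baselines, 22 complete patients per arm and a single Week 24 ANCOVA in place of the multiply imputed MMRM. The direction does not depend on these choices. The primary MMRM and the Hochberg test are untouched.

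**What to change.** In SAP 12.5.2.2.1, replace the death rule and the matching sentence in Step 3 with one rule: a subject who dies before a visit is assigned the largest log(ALP/baseline) observed at that visit across treatment arms, applied in Step 3 before the MMRM is fitted. This settles both the scale and the records used. In SAP 12.5.3.2, state the counterpart for the secondary estimands: the worst observed change from baseline at that visit for fatigue, and the largest log ratio to baseline for liver stiffness.

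The cost is a sentence in each place and a small programming change. No new data are needed, and the primary analysis stays as it is. The rule should be fixed before unblinding.
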